## 9. MEASUREMENT OF EFFECT

### 9.1 Antitumor Effect – Solid Tumors

For the purposes of this study, patients should be re-evaluated for response every 8 weeks per standard of care.

Response and progression will be evaluated in this study using the new international criteria proposed by the revised RECIST (version 1.1) [45]. Changes in the largest diameter (unidimensional measurement) of the tumor lesions and the shortest diameter in the case of malignant lymph nodes are used in the RECIST V1.1 criteria.

#### 9.1.1 Definitions

Evaluable for toxicity. All patients will be evaluable for toxicity from the time of first dose of study medication.

Evaluable for objective response. Only those patients who have measurable disease present at baseline, and have received at least 75% of the intended doses of cycle 1 of therapy, and have had their disease re-evaluated will be considered evaluable for response. These patients will have their response classified according to the definitions stated below. (Note: Patients who exhibit objective disease progression prior to the end of cycle 1 will also be considered evaluable.)

Evaluable Non-Target Disease Response. Patients who have lesions present at baseline that are evaluable but do not meet the definitions of measurable disease, have received at least one cycle of therapy, and have had their disease re-evaluated will be considered evaluable for non-target disease. The response assessment is based on the presence, absence, or unequivocal progression of the lesions.

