### 1.2 Secondary Objectives:

1.2.1 To evaluate the disease control rate after 8 weeks, 16 weeks and 24 weeks of treatment. Disease control rate is defined as the percentage of subjects who had a partial response post initial chemotherapy and who have a confirmed reduction in tumor size compared to post induction chemotherapy baseline (complete response, CR; partial response, PR) or fulfilling the criteria for stable disease (SD) according to Response Evaluation Criteria in Solid Tumors (RECIST V1.1). Patients with CR will be considered to have disease control if they continue to remain in CR since they do not have measurable disease at baseline.

1.2.2 To evaluate 1-year and 2-year overall survival. Overall survival is defined as the time from first dose of trial medication to date of death due to any cause.

1.2.3 To evaluate potential biomarkers for durability of response, especially tumor mutation burden (refer to Biomarker Section).

1.2.4 To assess the toxicity profile of experimental drug combination.

1.2.5 To evaluate objective response rate at 8 weeks, 16 weeks and 24 weeks. Objective response rate is the proportion of patients with complete response or partial response according to RECIST V1.1. Patients with CR at baseline will be excluded from objective response rate (ORR) analysis.

1.2.6 To evaluate quality of life (QOL). Quality of life is assessed by the validated, standardized EORTC questionnaires (specifically the QLQ-C30 and the LC-13) on screening/pre-study (for pre-treatment baseline), once during treatment, and at the end of treatment. These EORTC QOL measures are located in Appendix D.

1.2.7 To explore in a preliminary manner the response of genomic subsets to treatment focusing on tumor mutation burden, cMEK and TP53 mutation analysis of tumor tissue and evaluation of response, using the Oncology Research Information Exchange Network (ORIEN) consortium whole exome sequencing platform to evaluate tumor mutation burden, somatic and germline mutations.

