## 5.2 Nivolumab and Rucaparib Administration

The recommended starting dose of rucaparib as a continuously administered oral monotherapy is 600 mg BID. Patients may take rucaparib with or without food. Each dose should be taken with approximately 8 oz. (240 mL) of room temperature water. Tablets should be swallowed whole without crushing or chewing. Patients should take rucaparib doses as close as possible to 12 hours apart, preferably at the same time every day. If a patient misses a dose (i.e., does not take it within 4 hours of the scheduled time), the patient should skip the missed dose and resume by taking the next scheduled rucaparib dose. Missed or vomited doses should not be made up.

Modification of rucaparib dose may be a necessary component of AE management, and study-specific protocol guidelines for dose modifications should be followed. See Section 6.

Nivolumab will be administered as intravenous infusion once every 4 weeks at fixed dose of 480 mg. The FDA has approved a supplemental biologics license application adding a 4-week dosing schedule for nivolumab (Opdivo) across several of the PD-1 inhibitor's indications (non-small cell lung cancer, renal cell carcinoma, metastatic urothelial carcinoma, Hodgkin lymphoma, metastatic squamous cell carcinoma and hepatocellular carcinoma). Adding a q 4 weekly regimen will be convenient for patients and will be more cost effective as it will reduce number of visits to infusion center. We have had no problem with using q4 week dosing in SCLC at our center. No dose modification will be allowed (other than hold or discontinue). Please refer to Section 6 for guidance regarding Nivolumab schedule in response to toxicity.

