| Toxicity despite dose reduction steps to 200 mg BID or interruption of oral drug for > 14 consecutive days except if allowed if approved by the study medical monitor/designee. 
 
Prior to re-initiating treatment in a patient with a dosing delay > 14 days, the study medical monitor/designee must be consulted.
 
  |                                     | Discontinue                    |                      |                                |                                    |

Abbreviations: AE = adverse event; ALT = alanine aminotransferase; AML = acute myeloid leukemia; AST = aspartate aminotransferase; BID = twice daily; CTCAE = Common Terminology Criteria for Adverse Events; DILI = drug-induced liver injury; IV = intravenous; MDS = myelodysplastic syndrome; N/A = not applicable; ULN = upper limit of normal

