**For Patients with Measurable Disease (i.e., Target Disease)**

| Target Lesions | Non-Target Lesions          | New Lesions | Overall Response | Best Overall Response when Confirmation is Required* |
|----------------|-----------------------------|-------------|------------------|--|
| CR             | CR                          | No          | CR               | ≥4 wks. Confirmation**                               |
| CR             | Non-CR/Non-PD               | No          | PR               | ≥4 wks. Confirmation**                               |
| CR             | Not evaluated               | No          | PR               |  |
| PR             | Non-CR/Non-PD/not evaluated | No          | PR               |  |
| SD             | Non-CR/Non-PD/not evaluated | No          | SD               | Documented at least once ≥4 wks. from baseline**     |
| PD             | Any                         | Yes or No   | PD               | No prior SD, PR or CR                                |
| Any            | PD***                       | Yes or No   | PD               |  |
| Any            | Any                         | Yes         | PD               |  |

\*See RECIST V1.1 manuscript for further details on what is evidence of a new lesion.  
 \*\*Only for non-randomized trials with response as primary endpoint.  
 \*\*\*In exceptional circumstances, unequivocal progression in non-target lesions may be accepted as disease progression.  
Note: Patients with a global deterioration of health status requiring discontinuation of treatment without objective evidence of disease progression at that time should be reported as “*symptomatic deterioration.*” Every effort should be made to document the objective progression even after discontinuation of treatment.

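### The evaluable set in 9.1.1 drops patients who leave before any re-scan, which can only raise the objective response rate, and its 75% dose condition is not defined for two drugs

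*Combined protocol and SAP*

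**What the plan says.** - Section 9.1.1 admits to the objective-response set only patients with measurable disease at baseline who "have received at least 75% of the intended doses of cycle 1 of therapy, and have had their disease re-evaluated will be considered evaluable". One note softens this: "Patients who exhibit objective disease progression prior to the end of cycle 1 will also be considered evaluable".
- Section 1.2.5 sets the timepoints, "To evaluate objective response rate at 8 weeks, 16 weeks and 24 weeks", and states one exclusion: "Patients with CR at baseline will be excluded from objective response rate (ORR) analysis".
- Section 11.2 promises exact 95% binomial intervals for ORR. It names no analysis set, does not cite 9.1.1, and gives no rule for patients without a scan.
- Section 9.1 and the calendar in section 8 plan scans every 8 weeks on treatment. At the off-treatment visit CT is done only when clinically indicated, and later follow-up records survival only.
- The note under the measurable-disease table in 9.1.4.3 adds "Every effort should be made to document the objective progression even after discontinuation of treatment".
- On schedules, section 5.2 says "Nivolumab will be administered as intravenous infusion once every 4 weeks at fixed dose of 480 mg", with rucaparib taken twice daily without a break. Among the criteria for stopping rucaparib, Table 4 lists "interruption of oral drug for > 14 consecutive days", unless an exception is approved.

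**The concern.** Two of the three conditions in 9.1.1 are met or failed after treatment starts, so the outcome itself helps decide who is counted.

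The re-evaluation condition acts in one direction. A patient who never has a post-baseline scan cannot be scored CR or PR. Removing that patient shrinks the denominator and leaves the numerator alone. Patients lost this early are likely to include those doing worst, and a single-arm trial has no comparator in which the same loss would occur.

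The 75% dose condition is a separate problem. It can remove patients who were fully re-scanned, responders included, so it can move ORR up or down. It also cannot be applied as written, because the intended doses are not defined for one infusion plus a twice-daily tablet. Two analysts could report different rates and intervals from the same data.

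**Working it through.** **The plan's own figure.** The only precision figure given is in 11.1: with 36 patients and 50% progression-free at 6 months, a one-sided 90% lower limit of 38%. The exact (Clopper-Pearson) limit for 18 of 36 is the 0.10 quantile of Beta(18, 19), which is 38.2%. It reproduces. It concerns PFS and does not depend on the response set. No figure is given for ORR.

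**Who can drop out of the set.** Cycle 1 is taken as 28 days, from the 4-weekly nivolumab schedule and the calendar's placing of cycle 3 day 1 at about 2 months. The first planned scan is at week 8, so documenting progression inside cycle 1 would usually need an unscheduled scan. The early-progression note therefore rescues only part of the group. A patient who dies, withdraws or stops for toxicity before week 8 has no mandatory scan.

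**Direction of the re-evaluation condition.** With x responders among N patients and m unscanned patients removed, ORR goes from x/N to x/(N − m). It is multiplied by N/(N − m), which exceeds 1 whenever m > 0. It cannot fall.

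**Size.** The documents do not give the number with measurable disease, the number of responders or the number unscanned. Assumed for illustration: N = 30, x = 6, and m = 3 or 6. Intervals are exact two-sided 95%, as 11.2 specifies.

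| Set | ORR | 95% CI |
|---|---|---|
| All 30, unscanned counted as non-responders | 6/30 = 20.0% | 7.7 to 38.6 |
| 3 unscanned non-responders dropped | 6/27 = 22.2% | 8.6 to 42.3 |
| 6 unscanned non-responders dropped | 6/24 = 25.0% | 9.8 to 46.7 |
| 3 under-dosed, re-scanned patients dropped, 1 of them a responder | 5/27 = 18.5% | 6.3 to 38.1 |

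The first two exclusions add 2.2 and 5.0 percentage points. The interval on all 30 is 38.6 − 7.7 = 30.9 points wide. The last row shows that the dose condition can also lower ORR.

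**The 75% condition.** Cycle 1 holds 28 × 2 = 56 rucaparib doses and 1 nivolumab dose. Three quarters of 56 is 42, so a 7-day rucaparib gap sits exactly at the limit.

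| Rucaparib gap in cycle 1 | Rucaparib alone | Both drugs pooled (57) | Nivolumab alone |
|---|---|---|---|
| 8 days | 40/56 = 71.4% | 41/57 = 71.9% | 1/1 = 100% |
| 14 days | 28/56 = 50.0% | 29/57 = 50.9% | 1/1 = 100% |

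Gaps of 8 to 14 days do not exceed the 14-day limit in Table 4, so they can occur in patients who stay on treatment and are scanned. Such a patient fails the condition counted on rucaparib or on the pooled doses, and passes it counted on nivolumab.

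**The case against.** The strongest reply is that nothing is left open. Section 9.1.1 is the protocol's definition of who is evaluable for objective response, and 1.2.5 only adds that baseline CRs are out, which fits the requirement for measurable disease. Patients with no re-scan are then handled: they are not evaluable. Early progressors are retained, and the instruction in 9.1.4.3 to keep seeking objective progression shrinks the unscanned group further.

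Much of this stands. A reader might infer that 1.2.5 and 9.1.1 contradict each other. They need not: 1.2.5 does not say its exclusion is the only one, and 9.1.1 most naturally governs. But that reading is the one under which unscanned non-responders are removed. It settles which set applies without making it a good set, and it leaves the intended doses undefined.

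Three further inferences are not supported:

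- **That week-24 ORR would be taken only among patients scanned at that visit, which could inflate it greatly.** No section proposes that denominator. A patient who progressed at week 8 was re-evaluated and, if the dose condition is met, stays in the 9.1.1 set as a known non-responder.
- **That the disease control rate is biased in the same way.** Section 1.2.1 bases it on the "percentage of subjects who had a partial response post initial chemotherapy" plus CR patients who remain in CR, and 9.1.1 does not apply its conditions to it. Clearer denominator wording would help, but no bias follows.
- **That the remedy is to count every patient without baseline CR.** A patient in PR can enter with only small, non-measurable residual lesions. The non-measurable-disease table in 9.1.4.3 has no PR category, so such a patient would dilute ORR. The baseline measurable-disease condition should stay.

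**Conclusion.** The point holds for ORR. Followed as written, 9.1.1 removes certain non-responders from the denominator, which can only raise the estimate. Its dose condition gives different sets depending on the drug counted, with effects in either direction.

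The size is unknown. The illustrated rise of 2.2 to 5.0 points rests on the assumed 30 patients, 6 responders and 3 to 6 unscanned patients, and is small beside sampling error. A reader might infer that the trial's main result is at risk. It is not: ORR is secondary and descriptive, no decision threshold is attached to it, and the PFS analysis and the sample size of 36 are untouched. This is a cheap improvement, best made before the response data are analysed.

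**What to change.** In 11.2, with a cross-reference in 9.1.1:

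1. Make the main ORR denominator all treated patients with measurable disease (hence no CR) at baseline.
2. At each of weeks 8, 16 and 24, count as non-responders all patients with no post-baseline assessment and all with earlier progression or death.
3. State how a patient who was scanned earlier, has not progressed and misses a later scan is counted.
4. Keep the 9.1.1 evaluable set as a sensitivity analysis, and define its intended doses, either for each drug separately or for one named drug.

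The cost is a few sentences, with no new data or visits. The reported ORR may be slightly less favourable.

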#### 9.1.2 Disease Parameters

Measurable disease. Measurable lesions are defined as those that can be accurately measured in at least one dimension (longest diameter to be recorded) as  $\geq 10$  mm ( $\geq 1$  cm) with CT scan or MRI. All tumor measurements must be recorded in millimeters (or decimal fractions of centimeters).

Malignant lymph nodes. To be considered pathologically enlarged and measurable, a lymph node must be  $\geq 15$  mm ( $\geq 1.5$  cm) in short axis when assessed by CT scan (CT scan slice thickness recommended to be no greater than 5 mm [0.5 cm]). At baseline and in follow-up, only the short axis will be measured and followed.

Non-measurable disease. All other lesions (or sites of disease), including small lesions (longest diameter  $< 10$  mm [ $< 1$  cm] or pathological lymph nodes with  $\geq 10$  to  $< 15$  mm [ $\geq 1$  to  $< 1.5$  cm] short axis), are considered non-measurable disease. In addition, bone lesions, leptomeningeal disease, ascites, pleural/pericardial effusions, lymphangitis cutis/pulmonitis, inflammatory breast disease, and abdominal masses (not followed by CT or MRI), are considered as non-measurable disease.

Note: Simple cysts, defined as cystic lesions that meet the criteria for radiographically defined simple cysts, should not be considered malignant lesions (neither measurable nor non-measurable).

Conversely, ‘Cystic lesions’ thought to represent cystic metastases can be considered as measurable lesions, if they meet the definition of measurability described above. *However, if non-cystic lesions are present in the same patient, the preferred category is as target lesions.*

Target lesions. All measurable lesions up to a maximum of 2 lesions per organ and 5 lesions in total should be identified as **target lesions**, and will be recorded and measured at baseline. Target lesions should be selected on the basis of their size (lesions with the longest diameter), be representative of all involved organs, AND additionally should be lesions that lend themselves to reproducibly repeated measurements. For instance, if the largest lesion does not lend itself to reproducible measurement, then the next largest lesion which can be measured reproducibly should be selected as a target lesion.

A sum of the diameters (longest for non-nodal lesions, short axis for nodal lesions) for all target lesions will be calculated and reported as the baseline sum diameters. If lymph nodes are to be included in the sum, then only the short axis is added into the sum. The baseline sum diameters will be used as reference to further characterize any objective tumor regression in the measurable dimension of the disease.

Non-target lesions. All other lesions (or sites of disease) including any measurable lesions over and above the 5 target lesions should be identified as **non-target lesions** and should also be recorded at baseline. Additional measurement of these non-target lesions is not required, but the presence, absence, or in rare cases unequivocal progression of each non-target lesion should be noted throughout follow-up.

### 9.1.3 Methods for Evaluation of Measurable Disease

Conventional CT and MRI: This guideline has defined measurability of lesions on CT scan based on the assumption that CT slice thickness is 5 mm (0.5 cm) or less. If CT scans have slice thickness greater than 5 mm (0.5 cm), the minimum size for a measurable lesion should be twice the slice thickness. MRI is also acceptable in certain situations (*e.g.*, for body scans).

Use of MRI remains a complex issue. MRI has excellent contrast, spatial, and temporal resolution; however, there are many image acquisition variables involved in MRI, which greatly impact image quality, lesion conspicuity, and measurement. Furthermore, the availability of MRI is variable globally. As with CT, if an MRI is performed, the technical specifications of the scanning sequences used should be optimized for the evaluation of the type and site of disease. Furthermore, as with CT, the modality used at follow-up should be the same as was used at baseline and the lesions should be measured/assessed on the same pulse sequence. It is beyond the scope of the RECIST guidelines to prescribe specific MRI pulse sequence parameters for all scanners, body parts, and diseases. Ideally, the same type of scanner should be used and the image acquisition protocol should be followed as closely as possible to prior scans. Body scans should be performed with breath-hold scanning techniques, if possible.

### 9.1.4 Response Criteria

#### 9.1.4.1 Evaluation of Target Lesions

Complete Response (CR): Disappearance of all target lesions. Any pathological lymph nodes

(whether target or non-target) must have reduction in short axis to <10 mm (<1 cm).

Partial Response (PR): At least a 30% decrease in the sum of the diameters of target lesions, taking as reference the baseline sum diameters.

Progressive Disease (PD): At least a 20% increase in the sum of the diameters of target lesions, taking as reference the smallest sum on study (this includes the baseline sum if that is the smallest on study). In addition to the relative increase of 20%, the sum must also demonstrate an absolute increase of at least 5 mm (0.5 cm). (Note: the appearance of one or more new lesions is also considered progression).

Stable Disease (SD): Neither sufficient shrinkage to qualify for PR nor sufficient increase to qualify for PD, taking as reference the smallest sum diameters while on study.

#### 9.1.4.2 Evaluation of Non-Target Lesions

Complete Response (CR): Disappearance of all non-target lesions and normalization of tumor marker level. All lymph nodes must be non-pathological in size (<10 mm [ $<1$  cm] short axis).

Note: If tumor markers are initially above the upper normal limit, they must normalize for a patient to be considered in complete clinical response.

Non-CR/Non-PD: Persistence of one or more non-target lesion(s) and/or maintenance of tumor marker level above the normal limits.

Progressive Disease (PD): Appearance of one or more new lesions and/or *unequivocal progression* of existing non-target lesions. *Unequivocal progression* should not normally trump target lesion status. It must be representative of overall disease status change, not a single lesion increase.

Although a clear progression of “non-target” lesions only is exceptional, the opinion of the treating physician should prevail in such circumstances, and the progression status should be confirmed at a later time by the review panel (or PI).

#### 9.1.4.3 Evaluation of Best Overall Response

The best overall response is the best response recorded from the start of the treatment until disease progression/recurrence (taking as reference for progressive disease the smallest measurements recorded since the treatment started). The patient's best response assignment will depend on the achievement of both measurement and confirmation criteria.

**For Patients with Measurable Disease (i.e., Target Disease)**

| Target Lesions | Non-Target Lesions          | New Lesions | Overall Response | Best Overall Response when Confirmation is Required* |
|----------------|-----------------------------|-------------|------------------|--|
| CR             | CR                          | No          | CR               | ≥4 wks. Confirmation**                               |
| CR             | Non-CR/Non-PD               | No          | PR               | ≥4 wks. Confirmation**                               |
| CR             | Not evaluated               | No          | PR               |  |
| PR             | Non-CR/Non-PD/not evaluated | No          | PR               |  |
| SD             | Non-CR/Non-PD/not evaluated | No          | SD               | Documented at least once ≥4 wks. from baseline**     |
| PD             | Any                         | Yes or No   | PD               | No prior SD, PR or CR                                |
| Any            | PD***                       | Yes or No   | PD               |  |
| Any            | Any                         | Yes         | PD               |  |

\*See RECIST V1.1 manuscript for further details on what is evidence of a new lesion.  
 \*\*Only for non-randomized trials with response as primary endpoint.  
 \*\*\*In exceptional circumstances, unequivocal progression in non-target lesions may be accepted as disease progression.  
Note: Patients with a global deterioration of health status requiring discontinuation of treatment without objective evidence of disease progression at that time should be reported as “*symptomatic deterioration.*” Every effort should be made to document the objective progression even after discontinuation of treatment.

